5.2. DESIGN CONSIDERATIONS, SAMPLE SIZE, AND POWER ESTIMATES

5.2.1. Overall Trial Design

During our initial sample size analyses, we considered trial designs that would power two hypothesis tests: one test for the weaning effect of morphine and one test for the weaning effect of methadone. These designs accounted for multiple comparison adjustment (adjusted for two comparisons) and unadjusted comparisons. When we adjusted the two comparisons for multiple comparisons using a Bonferroni adjustment, we rejected a test if the p-value is ≤ 0.025 , and we would require at least 1,032 randomized infants for 90% power. If we did not use an adjustment, then the required sample size was still at least 826 randomized infants. In both cases, the assumed standard deviation was 6.9 days. If the standard deviation is larger, then in both cases the required sample sizes would be even larger. Given the low probability of enrolling around 1,000 infants, we chose a design that would compare weaning interventions regardless of drug used (morphine/methadone). Given that the chosen design would primarily focus on estimating the weaning intervention effect regardless of drugs, we added two secondary analyses examining the intervention effect within each drug (Secondary Outcomes 1 and 2). In addition to frequentist analyses of Secondary Outcomes 1 and 2, Bayesian analyses are planned to derive evidence that may be clinically meaningful from the limited data available for each drug.

5.2.2. Compatibility with the ESC Trial

We expect that a substantial number of sites in the IDeA States Pediatric Clinical Trials Network and NRN may participate in both this trial and the concurrent Eat, Sleep, and Console (ESC) trial, a stepped-wedge cluster randomized controlled trial that will compare the ESC care approach to usual institutional care with the Finnegan Neonatal Abstinence Scoring Tool (FNAST) or modification thereof. Thus, babies enrolled into the Weaning trial may also be co-enrolled into ESC. This situation presents both statistical benefits and challenges.

The benefits of co-enrollment with the ESC trial mainly derive from better control over variability in site practice differences (that are apparent from the results of the ACT NOW Current Experience Study—a medical record abstraction of 1808 opioid-exposed neonates across 30 clinical centers) that would not otherwise be possible outside of the ESC trial. Specifically, clinical sites have a wide range of practice differences, and there are indications that practice may be drifting increasingly towards ESC because of

the currently well documented limitations of the FNAST approach. This is an especially pertinent issue for the Weaning trial because of its relatively long expected enrollment period of 3.3 years. Without co enrollment into the ESC trial, we may have difficulty knowing when and how site practices imperceptibly shift from FNAST to ESC and the different variations thereof, and imbalance in such site practices could make it difficult to achieve overall balance on this criterion across the Weaning treatment arms. This will likely increase center differences, potentially in an imbalanced manner, increasing the overall variability in the data, which makes it more difficult to detect a treatment signal.

In contrast, co-enrollment into the ESC trial will allow us to precisely know when groups of sites switch over to ESC from FNAST, with all sites having transitioned to the ESC care tool at the end of that trial, which will have a shorter duration than the Weaning trial. Together with randomization within site for Weaning, this ensures that we have precise and detailed information on site practices at all times through the duration of the ESC trial, increased opportunity to achieve overall balance for this aspect of clinical practice across the Weaning treatment arms, and more uniformity in site practices at the end of the trial. This will reduce center differences and provide more detailed information on center practices over time which will reduce the overall variability in the data.

The challenges of co-enrollment mainly involve potential confounding issues between the different interventions being tested across the different trials and any biases that may thus result. However, confounding is less of a concern here because of the following reasons:

- a) The two interventions in the two trials are applied at different levels – Weaning tests an individualized intervention whereby each baby within a center is randomized. ESC tests a practice change at the center level using a stepped wedge design, whereby entire groups of sites switch to ESC according to a randomized schedule.
- b) Bias will be further minimized by ensuring that the Weaning trial randomizes individual babies within each site (regardless of when it is scheduled to switch over to ESC), using a block randomization approach to assure a relatively equal distribution of babies in each arm within each center within a unit of time. In contrast, ESC uses block randomization (using time as a blocking factor) to randomize entire groups of sites to switch over to ESC.

In order to further address concerns regarding confounding and bias, we will conduct sensitivity analyses by adding a variable that represents whether a baby in the Weaning trial was 1) in the FNAST stage of the ESC trial, 2) in the ESC stage of the ESC trial, or 3) was at a site that was not participating in the ESC trial as a covariate and potential effect modifier for babies in the Weaning trial.

5.2.3. Sample Size and Power Estimates

Eligible infants are those in the ISPCTN and NRN sites that clinical teams are pharmacologically treating for NOWS with an opioid as the primary drug treatment and have a gestational age ≥ 36 weeks (see **Section 4.1**). We used the most recent randomized trial comparing morphine to methadone to determine sample size and power estimates (18). In that trial, researchers enrolled 116 pharmacologically treated NOWS infants from February 2014 until March 2017. The research team randomly allocated 58 infants to morphine treatment and 58 infants to methadone treatment. The standard deviation for the morphine arm was 6.9 days, while the standard deviation for the methadone arm was 8.0 days. We used these statistics to derive sample size estimates (**Table 6**). The total sample size estimates given in Table 6 assume that the clinical team will treat 70% of enrolled infants with

morphine. This trial will enroll a total of 502 infants (251 infants to each of the rapid and slow wean interventions) irrespective of the proportion of infants treated with morphine or methadone.

Table 6. Sample Size Estimates

Power	N per Arm	Total N	Morphine* N	Methadone* N	LOT-difference	SD	alpha
0.9	251	502	352	150	2	6.9	0.05
0.9	296	592	414	178	2	7.5	0.05
0.9	337	674	472	202	2	8.0	0.05
0.85	214	428	300	128	2	6.9	0.05
0.85	253	506	354	152	2	7.5	0.05
0.85	288	576	403	173	2	8.0	0.05
0.80	187	374	262	112	2	6.9	0.05
0.80	221	442	309	133	2	7.5	0.05
0.80	252	504	353	151	2	8.0	0.05

*includes infants randomized to either rapid-wean or slow-wean interventions
 ‡LOT: length of treatment days

A difference of 2.0 days in the length of treatment represents the minimum clinically important treatment effect for clinical care. If we can demonstrate a 2.0-day difference, there will likely be a reduction in hospital resources (bed, nursing, pharmacy, and physician) and cost. In addition, this effect size should facilitate a faster transition out of the hospital and keep the maternal-infant dyad together in a better environment than a hospital. The proposed intervention difference is similar to a recent trial comparing morphine to methadone (18). Group sample sizes of 251 infants per treatment arm (total enrollment, 502 infants) will achieve 90% power to reject the null hypothesis of equal means when the population difference is 2.0 days with a standard deviation of 6.9 days and with a significance level of 0.05 using a two-sided two sample t-test. If the standard deviation is as high as 8.0 days, a similar sample size will achieve 80% power to reject the null hypothesis using a two-sample t-test and a two-sided significance level of 0.05.

With respect to analysis of the Bayley IV at 24 month follow-up, if the FU is at least 60%, then with a two-sided alpha of 0.05 we will be able to detect a difference in any composite score of 5.7 or greater with at least 80% power and will be able to detect a difference in any scaled score of 1.06 with at least 80% power.

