3.4 Sample Size

The projected effect size is a 2.0-day difference in the duration of opioid treatment between infants randomized to a rapid-wean intervention and infants randomized to a slow-wean intervention. The sample size was derived by using results from a recently completed trial comparing morphine-treated infants and methadone-treated infants in which the standard

deviation was 6.9 days for the morphine-treated infants and 8.0 days for methadone-treated infants (see protocol for more details). A standard deviation of 6.9 days was used to derive the sample size, anticipating that more infants will be treated with morphine. However, the primary analysis compares treatment regardless of drug used, and sample size was calculated irrespective of the proportion of infants treated with morphine or methadone.

The study will have two intervention arms (rapid-wean and slow-wean) with 251 morphine/methadone treated infants per intervention arm, for a total of 502 morphine/methadone treated infants. This will achieve 90% power to reject the null hypothesis with a significance level of 0.05 using a two-sided two-sample t-test. The null hypothesis will be morphine or methadone treated infants in both arms will have equal means when the population difference in the duration of opioid treatment is 2.0 days with a standard deviation of 6.9 days. Sample size recalculation was performed in July 2022, using a standard deviation of 6.2 based on data from enrolled infants up to June 2022. It was determined that a sample size of 404 is needed to reach 90% power to reject the null hypothesis with a significant level of 0.05 using a two-sided two-sample t-test, and 302 to reach 80% power. We chose this latter number as our target enrollment.

Subsequently, given continued enrollment challenges faced by this trial, the DSMC and NICHD decided to terminate the trial after December 31, 2023.

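### The current protocol still gives 502 infants and 90% power as its operative figures, although the SAP records a re-estimated target of 302 at 80% power and closure on a fixed date

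*Protocol*

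**What the plan says.** Protocol 5.2.3 states without condition that "This trial will enroll a total of 502 infants", split as "251 infants to each of the rapid and slow wean interventions". It says this size "will achieve 90% power to reject the null hypothesis of equal means when the population difference is 2.0 days". The inputs behind that claim are an SD of 6.9 days and a two-sided t-test at the 5% level. The same section explains the choice of effect: "A difference of 2.0 days in the length of treatment represents the minimum clinically important treatment effect". Section 1.8 repeats the size and power. Sections 1.9 and 5.4 derive a recruitment time of 3.3 years from 502, and 5.4 a monthly rate of 12 to 13 infants.

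The protocol also plans a change. Sections 1.8 and 5.2.4 provide for a recalculation at 25% accrual from the pooled SD, without unblinding. Section 1.9 makes its projection conditional on an unchanged sample size.

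SAP 3.4 first restates 251 per arm, 502 in total and 90% power. It then reports the July 2022 recalculation at SD 6.2: 404 infants for 90% power, 302 for 80%. Of the 302 it says: "We chose this latter number as our target enrollment". It adds that, because enrolment remained difficult, "the DSMC and NICHD decided to terminate the trial after December 31, 2023".

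On dates, SAP 1.2 cites protocol V-10 of 26 May 2023, and SAP version 2.0 is dated 26 February 2024. The protocol supplied is Version 11, whose change log mentions an event at the end of August 2024. The log entries for Versions 10 and 11 list no sample-size change.

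**The concern.** The latest protocol was issued after the re-estimation and after the planned end of enrolment, yet its body still describes a larger and better-powered trial than the one the SAP describes. SAP 3.4 corrects the target but leaves the original statement standing beside it in the future tense. It gives neither the number randomised nor the difference that number could detect.

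What is at stake is how a non-significant result is read. The protocol treats 2.0 days as the smallest difference that matters clinically. A reader who takes 90% power at face value assumes a 10% chance of missing it. At the revised target that chance is 20%, twice as large, and it is larger still if fewer than 302 were enrolled.

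**Working it through.** **Inputs.** Difference d = 2.0 days, two-sided alpha 0.05, two-sample t-test, 1:1 allocation (protocol 5.2.3). SD 6.9 (protocol 5.2.3) and SD 6.2 (SAP 3.4).

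**Formula.** Infants per arm: n = 2 (z_0.975 + z_power)² (SD/d)², with z_0.975 = 1.960, z_0.90 = 1.282 and z_0.80 = 0.842. The squared sums are 10.507 for 90% power and 7.849 for 80%.

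**The plan's own figures**
- Protocol, SD 6.9, 90%: 2 × 10.507 × 3.45² = 250.1, so 251 per arm and 502 in total. Power at 251 per arm by the noncentral t is 0.900. All nine rows of protocol Table 6 also reproduce.
- SAP, SD 6.2, 90%: 2 × 10.507 × 3.1² = 201.9, so 202 per arm and 404 in total.
- SAP, SD 6.2, 80%: 2 × 7.849 × 3.1² = 150.9, so 151 per arm and 302 in total.

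The noncentral t gives 203 and 152 per arm for the two SAP cases, a trivial difference.

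**Where the reduction comes from.** 302/502 = 60%. The smaller SD accounts for 502 to 404 at unchanged power. The step from 404 to 302 lowers power from 90% to 80%.

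**Power and precision at SD 6.2.** The standard error of the difference is SE = 6.2 × √(2/n). Power for 2.0 days is from the noncentral t. The detectable difference at 80% power is (1.960 + 0.842) × SE, and the expected 95% CI half-width is about 1.96 × SE.

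| Total N | SE (days) | Power for 2.0 days | Detectable at 80% (days) | CI half-width (days) |
|---|---|---|---|---|
| 404 (90% option in SAP 3.4) | 0.617 | 89.9% | 1.7 | 1.2 |
| 302 (SAP target) | 0.714 | 79.8% | 2.0 | 1.4 |
| 250 (assumed) | 0.784 | 71.9% | 2.2 | 1.5 |
| 200 (assumed) | 0.877 | 62.2% | 2.5 | 1.7 |

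The last two rows illustrate a possible shortfall; neither document gives these numbers. All rows take N as infants with an analysed primary outcome and ignore any effect of the random site term.

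**The case against.** The case against is substantial. No calculation is wrong. The protocol treats 502 as open to revision: 1.8 and 5.2.4 announce the recalculation, 1.9 is expressly conditional, 5.4.1 foresees an accrual review that could end the trial, and 5.1.6 prepares Bayesian analyses in case enrolment is insufficient. SAP 3.4 openly reports the new SD, target, power and end date. The analysis will give the mean difference with a 95% confidence interval and a posterior probability, and the CONSORT diagram will show the numbers randomised (SAP 6.4.1 and 6.5.1). Those intervals show directly whether 2 days is excluded. Enrolment is over, so an amendment cannot alter conduct.

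Most of this stands, and it limits how serious the point is. It does not rescue the protocol text: the statement in 5.2.3 carries no condition, the protocol never reports the outcome of its own reassessment, and versions issued after July 2022 left the figures untouched.

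A reader might infer more than the documents support:
- **That the target was cut improperly or out of sight.** Protocol 5.2.4 plans the re-estimation as a blinded one needing no alpha adjustment, and the SAP discloses the result.
- **That enrolment is known to have fallen short of 302, or that the trial closed whatever its size.** Neither is stated. A shortfall is only suggested by the enrolment difficulties in SAP 3.4 and the sample-size limitation mentioned in SAP 6.5.1.
- **That power at 302 should be judged at SD 6.9, giving about 71%.** Protocol 5.2.4 says that SD describes the whole treatment course and expects a smaller one for weaning alone. The in-trial estimate of 6.2 replaced it.

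**Conclusion.** The point holds as a consistency defect. Protocol 1.8 and 5.2.3, and the recruitment figures in 1.9 and 5.4, present 502 infants and 90% power as operative when the target had become 302 at 80%. At the SAP's own SD of 6.2, 90% power needs 404, so it is not attained at 302 or below. The firm size of the discrepancy is 79.8% against a stated 90%, with 60% of the stated number of infants. This relies only on the target and SD in SAP 3.4. Anything lower, such as 72% at 250 or 62% at 200, depends on an assumed final number. The consequence is for interpretation and reporting, and the SAP's disclosure already removes part of it.

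**What to change.** - **Protocol 1.8 and 5.2.3:** replace 502 and 90% as the operative figures with the re-estimated SD of 6.2, the target of 302 at 80% power and the closing date, citing SAP 3.4. Keep 502 and 90% only as the original design assumption.
- **Protocol 1.9 and 5.4:** make the target and recruitment projection consistent with this, or label them as the original projection.
- **SAP 3.4:** mark 502 and 90% as superseded. Add the number actually randomised, with the resulting detectable difference or expected 95% CI width. The rest of the restatement is already there.

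The cost is a text amendment and a less favourable stated power. Conduct, patient numbers and the planned analyses do not change.

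### The Bayley-4 detectable differences in Protocol 5.2.3 (5.7 composite, 1.06 scaled) belong to the 502-infant plan, give no SD, and were not restated when the target fell to 302

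*Protocol*

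**What the plan says.** Protocol 5.2.3 first sizes the trial on the primary outcome: "Group sample sizes of 251 infants per treatment arm (total enrollment, 502 infants". The next paragraph turns to the Bayley at 24 months. Its condition is a follow-up floor, "if the FU is at least 60" per cent. On that condition it claims at least 80% power at two-sided alpha 0.05: "we will be able to detect a difference in any composite score of 5.7 or greater", and "detect a difference in any scaled score of 1.06 with at least 80% power". It gives no Bayley SD and no number assessed.

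SAP 3.4 reports a recalculation in July 2022, made for the primary outcome only with an SD of 6.2 days. It gives 404 infants for 90% power, "and 302 to reach 80% power. We chose this latter number as our target enrollment". It then says that the DSMC and NICHD decided to end the trial after December 31, 2023, and gives no final number enrolled. The SAP states no Bayley power or detectable difference.

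The Bayley-4 is the endpoint that Protocol Table 1 lists for the infant-development secondary objective. The SAP tests its cognitive, language and motor scores under H13 (section 2.2.1, Research Objective 13).

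**The concern.** The Bayley sentence gives a power for a sample that the trial no longer aims to reach. At the stated 60% follow-up, 502 enrolled gives 301 children assessed and 302 enrolled gives 181. The protocol text was not updated, although its latest change summary (version 10 to 11) cites an event of August 2024, after both the cut in target and the decision to end the trial.

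The stake is interpretation. Anyone who takes the trial's sensitivity for development from the protocol will find 5.7 and 1.06. They would judge the H13 comparisons against differences for which the power at 302 is probably well below 80%. Because no Bayley SD is given, the reader cannot correct the figures.

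**Working it through.** **Inputs.** From Protocol 5.2.3: two-sided alpha 0.05, power 80%, differences 5.7 and 1.06, follow-up 60%, 502 infants in two equal arms. From SAP 3.4: target 302. Number assessed per arm: 502 × 0.60 / 2 = 150.6, and 302 × 0.60 / 2 = 90.6. The Bayley SDs are not in the documents. SDs of 15 (composite) and 3 (scaled) are my assumption, shown within ranges of 13 to 18 and 2.5 to 3.5.

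**Formula.** Detectable difference MDD = (1.960 + 0.842) × SD × sqrt(2/n), with n per arm. The table uses the exact two-sample t-test, which differs from this by about 0.04 composite points at most.

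**Check of the enrolment targets.** n per arm = 2 × (z-sum × SD / 2.0)².
- SD 6.9, 90% power: 251, so 502.
- SD 6.2, 90% power: 202, so 404.
- SD 6.2, 80% power: 151, so 302.

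All three agree with the documents.

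**The plan's own Bayley figures.** Without an SD they cannot be strictly reproduced, but they can be solved backwards. At n = 150.6, MDD/SD = 2.802 × sqrt(2/150.6) = 0.323. Then 5.7/0.323 gives an SD of about 17.6, and 1.06/0.323 about 3.3 (17.60 and 3.27 by the exact t-test). So at 502 the claim of at least 80% power is true for SDs up to about 17.6 and 3.27. With SDs of 15 and 3, power at 502 is 91% and 86%.

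**Effect of the cut, for any SD.** MDDs grow by sqrt(502/302) = 1.289. If the stated values were the exact 80%-power values:
- 5.7 × 1.289 = 7.35
- 1.06 × 1.289 = 1.37
- power for the stated differences = Φ(2.802/1.289 − 1.960) = Φ(0.213) = 58%

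**By SD, at 60% follow-up (exact t-test).**

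| Score | SD | MDD at 502 | Power for stated difference at 502 | MDD at 302 | Power for stated difference at 302 |
|---|---|---|---|---|---|
| Composite | 13 | 4.21 | 96.7% | 5.44 | 83.5% |
| Composite | 15 | 4.86 | 90.8% | 6.28 | 72.0% |
| Composite | 17.6 | 5.70 | 80.0% | 7.37 | 58.2% |
| Composite | 18 | 5.83 | 78.2% | 7.53 | 56.4% |
| Scaled | 2.5 | 0.810 | 95.6% | 1.046 | 81.0% |
| Scaled | 3 | 0.972 | 86.4% | 1.255 | 65.7% |
| Scaled | 3.27 | 1.06 | 80.0% | 1.370 | 58.3% |
| Scaled | 3.5 | 1.134 | 74.5% | 1.465 | 52.7% |

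**What would rescue the claim at 302.**
- *A smaller SD.* At 90.6 per arm, 80% power for 5.7 and 1.06 needs SDs of about 13.6 and 2.5 or lower. The same differences would then have had about 95% power at 502.
- *Higher follow-up.* With SDs of 15 and 3 (normal approximation), n per arm is 2 × (2.802 × 15/5.7)² = 109 and 2 × (2.802 × 3/1.06)² = 126. That is 218/302 = 72% and 252/302 = 83% follow-up. With the back-solved SDs it is 301 of 302, essentially everyone.

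**The case against.** The strongest reply is that nothing was miscalculated. The sentence sits in the 502-infant section, and at 502 it is true for any SDs up to about 17.6 and 3.27. It says at least 60% follow-up, so 60% is a floor, and at 302 a smaller SD or better retention could still deliver the figures. With a composite SD of 15 and 70% follow-up, the detectable difference is 5.81, close to 5.7. The analysis will report mean differences with 95% confidence intervals (Protocol 5.1.5, SAP 6.4.1), and these show what is excluded better than a planning figure does. SAP 6.4.4 calls all analyses other than the primary exploratory. Covariate adjustment might recover some precision. Most of this stands, and it limits the point to a planning statement that was not carried forward.

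It does not remove the point. The stated condition is 60%, and at 60% of 302 the figures need SDs low enough that the same differences would have had about 95% power at 502. That is hard to square with a sentence quoting 80%.

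A reader might infer three stronger things that the documents do not support.
- *That 5.7 and 1.06 come from different calculations*, since SDs of 15 and 3 would imply 218 and 252 children assessed. This depends on a 5:1 SD ratio that is not in the documents. SDs of about 17.6 and 3.27 give both figures at 502 and 60%.
- *That the Bayley is the trial's main long-term safety evidence.* The protocol places development among its other secondary outcomes. The safety outcomes are seizures, stool output, respiratory disturbances and feeding tolerance.
- *That 6.3 and 1.26 are the correct replacements.* They rest on assumed SDs. If the sponsor's own SDs were 17.6 and 3.27, the values would be nearer 7.4 and 1.37.

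**Conclusion.** The point holds as a statement not carried over to the revised target. For any SD, the detectable differences at 302 are 1.29 times those at 502 for the same follow-up rate. Power for the stated differences at 302 and 60% follow-up is about 58% if they were the exact 80%-power values at 502, and 72% (composite) and 66% (scaled) with assumed SDs of 15 and 3. It reaches 80% only with SDs of about 13.6 and 2.5 or lower, or with follow-up well above 60%.

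The result rests on a simple two-sample comparison without site effects or covariates, and on SDs that the documents do not give. The final number enrolled is not stated; if it is below 302, the shortfall is larger. This concerns a secondary outcome, and the primary calculation at 302 is unaffected.

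**What to change.** In Protocol 5.2.3, and in the SAP under H13:
- State the composite and scaled SDs that the sponsor used, and their source.
- Restate the detectable differences at 80% power and two-sided alpha 0.05 for the number actually enrolled, in a short table by follow-up rate (for example 60%, 70%, 80% and 90%).
- Mark the 5.7 and 1.06 figures as belonging to the 502-infant plan.

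The table should use the sponsor's SDs; the values in this note are illustrations.

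The cost is a text change and a less favourable stated figure for a secondary outcome. No procedure, enrolment or analysis changes. SAP 3.7 expects the follow-up analysis to start in July 2026, so on that timetable the restatement can be in place before the Bayley results are analysed.
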